|------------------------------------|---|

| | |
|--|---|
| | 
The goal for the IP is that the mean \log_{10} reduction of all four primary objectives meets the following criteria:
 
 1. The lower limit of the 95% confidence interval (two-sided) of mean log reduction at 30 seconds will be greater than or equal to 2 for the abdomen. 2. The lower limit of the 95% confidence interval (two-sided) of mean log reduction at 30 seconds will be greater than or equal to 3 for the groin. 3. The lower limit of the 95% confidence interval (two-sided) of mean log reduction at 6 hours will be greater than or equal to 2 for the abdomen. 4. The lower limit of the 95% confidence interval (two-sided) of mean log reduction at 6 hours will be greater than or equal to 3 for the groin 
The HC testing requirements will only be considered met when and only when all four primary objectives pass HC analysis acceptance criteria. No multiplicity adjustment is required.
 
The RS should meet the same efficacy standards as the IP.
 
HC Exploratory Analysis: 1) The following descriptive statistics for \log_{10} CFU/cm² reductions will be computed for the IP and RS, grouped by anatomical site and each post application sampling for the 10 minute time point: mean, median, standard deviation, minimum, maximum, and count. The 95% confidence intervals (two-sided) will be calculated for the observed log reductions for the IP and RS at the 10 minute time point on each anatomical area.
 
2) \log_{10} CFU/cm² reductions at 30 seconds, 10 minutes, and 6 hours on the abdomen and the groin for the IP will be compared to the RS using two-sample t-test.
 
FDA Efficacy Analyses
 
FDA Primary Analysis: A linear regression model for each body site (abdomen and groin) will be used for primary analysis of efficacy at 10 minutes. In the model, the response is the post-product application bacterial counts at 10 minutes and predictors are the study products as a fixed effect and the pre-product application bacterial loads as a covariate. The ATE corrected for pre-product application bacterial loads will be estimated from the model and compared to both non-inferiority and superiority criteria.
 
The FDA testing requirements for the primary analysis will only be considered met when and only when all four primary objectives (10 minutes for both abdomen and groin) pass FDA analysis acceptance criteria, no multiplicity adjustment is required.
 
To evaluate the persistent antimicrobial properties of a single Swabstick impregnated with 2% (w/v) chlorhexidine gluconate in 70% (v/v) isopropyl alcohol, \log_{10} bacterial counts at 6 hours post product application for each product application site will be converted to a binary (yes or no) success measure with success defined as having skin flora counts that are less than or equal to the baseline skin flora counts. Responder rates at 6 hours post product application will be summarized descriptively for each
 |

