|--|---|

| | |
|--|---|
| | 
product on each body site. No inferential analysis will be performed on the 6 hour time point data.
 
FDA Secondary Analysis: The secondary objectives will be evaluated only when the four co-primary objectives pass both non-inferiority and superiority criteria. A linear regression model for the abdomen will be used for a secondary analysis of efficacy at 30 seconds. In the model, the response is the post-product application bacterial counts at 30 seconds and predictors are the study products as a fixed effect and the pre-product application bacterial loads as a covariate. The ATE corrected for pre-product application bacterial loads will be estimated from the model and compared to both non-inferiority and superiority criteria.
 
FDA Exploratory Analyses: The following descriptive statistics for \log_{10} CFU/cm² reductions will be computed for the IP, AC and NC at each anatomical site at 30 seconds, 10 minutes, and 6 hours post product application: mean, median, standard deviation, minimum, maximum, and count.
 
Product weight expression will be calculated as product weight prior to product application (g) – product weight post-product application (g). The following descriptive statistics for expression weight will be computed for each product at each anatomical site: mean, median, standard deviation, minimum, maximum, and count.
 |
|--|---|

Table of Contents

SUMMARY 4

LIST OF ABBREVIATIONS AND DEFINITION OF TERMS 14

1.0 INTRODUCTION 15

2.0 OBJECTIVES 15

 2.1 Safety Objectives.....15

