3.3 Product Application Allocation and Methods to Reduce Bias

3.3.1 Randomization

The randomization scheme for the study will be provided by the Sponsor. A sufficient number of subjects will be recruited and newly randomized to meet the minimum number of evaluable product application sites per study product arm, preserving the randomization assignment. The number of evaluable product application sites per study product arm per anatomical area will be monitored to determine additional subject enrollment and randomization to meet the required evaluable sample size. Subjects who fail to meet Product Application Day baselines will not be replaced. Additional subjects will be randomized to account for product application day failures.

Subjects will be randomized to study product arms using the following block design:

Study Product Balance

Each subject will receive two different study products, one on the right side of the body and one on the left. Therefore, there are six possible study product combinations: A-B, A-C, A-D, B-C, B-D and C-D.

A minimum of 516 evaluable subjects will be required to achieve a total of a minimum of 192 evaluable product application sites for groin and abdominal regions for 60% (v/v) 1-propanol (RS) and 280 evaluable product application sites for groin and abdominal regions for the other three study product arms. Due to the imbalance of the sample size between RS and other products, RS cannot be blinded. Assuming the treatment code for RS is B and all the other three products are either A, C or D, within each small block [i.e., every 129 (516/4) evaluable subjects randomized], number of subjects who receive each product combination is shown below. With 4 blocks in total (i.e., 516 evaluable subjects), the minimum of 192 evaluable product application sites for groin and abdominal regions for 60% (v/v) 1-propanol (RS) and 280 evaluable product application sites for groin and abdominal regions for the other three study product arms can be achieved.

| Product Combination | No. of Subjects in Each Block |
|---------------------|-------------------------------|
| A-B | 16 |
| A-C | 27 |
| A-D | 27 |
| B-C | 16 |
| B-D | 16 |
| C-D | 27 |
| Total | 129 |

Left/Right Balance

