4.0 STUDY POPULATION

Healthy male and female volunteers, 18 years of age or older, with no dermatological conditions or known history of sensitivity to natural rubber latex, adhesive skin products (e.g., Band-Aids, medical tapes), isopropyl alcohol or chlorhexidine gluconate will be enrolled into this study. A sufficient number of volunteers will be enrolled such that a minimum number of evaluable product application sites are available for the groin (sebaceous rich) region and the abdominal (sebaceous poor) region for each of the study products. A minimum of 280 evaluable sites per anatomical location is required for the IP, AC, and NC. A minimum number of 192 evaluable site per anatomical location is required for the RS.

The minimum number of volunteers enrolled will be 516 based on the objective to assess four study product arms on the required number of unique skin sites for the groin and abdomen. Subjects must satisfy all Screening Day and Product Application Day Inclusion/Exclusion Criteria prior to Product Application Day procedures.

Subjects must qualify on all four abdomen and inguinal sites to be admitted into the study until such time that one of the anatomical sites has completed the minimal required evaluable sites, then subjects will be screened and treated on the remaining anatomical site. To be included in the primary analysis (modified Intent to Treat (mITT) data set), a product application site must have a Product Application Day microbial baseline within the stated requirements. Enrollment will continue until a minimum number of subjects meeting baseline criteria on each anatomical site per study product arm is identified.

Subjects will be treated utilizing bilateral applications to ensure that the study products will be evaluated on the sites as described in Table . Each subject has four independent product application sites: left and right sides for the abdomen and left and right sides for the groin.

| Arm | Study Product | Number of Abdomen Evaluations | Number of Groin Evaluations |
|-------------------------|---|--------------------------------------|------------------------------------|
| Investigational Product | Single Swabstick impregnated with 2% (w/v) chlorhexidine gluconate (CHG) in 70% (v/v) isopropyl alcohol | 280 | 280 |
| Reference Standard | 60% 1-propanol applied with a single Swabstick | 192 | 192 |
| Negative Control | 0.9% normal saline applied with a single Swabstick | 280 | 280 |

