13.5.3 FDA Primary Analysis

A linear regression model for each body site (abdomen and groin) will be used for primary analysis of efficacy at 10 minutes. In the model, the response is the post-product application bacterial counts at 10 minutes and predictors are the study products as a fixed effect and the pre-product application bacterial loads as a covariate. The ATE corrected for pre-product application bacterial loads will be estimated from the model and compared to both non-inferiority and superiority criteria.

For assessment of the primary objectives (i.e., immediate activity at 10 minutes post application on the abdomen and groin):

A non-inferiority criterion with a 0.5 \log_{10} margin will be implemented for the average treatment effect (ATE) of the IP compared to the AC (i.e., the upper two-sided 95% confidence bound of the post-product application bacterial load corrected for pre-product application bacterial load of the IP – AC should be less than 0.5 \log_{10}).

A 1.2 \log_{10} superiority criterion will be implemented for the ATE of the IP compared to the NC (i.e., the lower two-sided 95% confidence bound of the post-product application bacterial load corrected for pre-product application bacterial load of the NC – IP should be greater than 1.2 \log_{10}).

To evaluate the persistent antimicrobial properties of a single Swabstick impregnated with 2% (w/v) chlorhexidine gluconate in 70% (v/v) isopropyl alcohol, \log_{10} bacterial counts at 6 hours post product application for each product application site will be converted to a binary (yes or no) success measure with success defined as having skin flora counts that are less than or equal to the baseline skin flora counts. Responder rates at 6 hours post product application will be summarized descriptively for each product on each body site. No inferential analysis will be performed on the 6 hour time point data.

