13.5.4 FDA Secondary Analysis

A linear regression model for the abdomen will be used for the analysis of efficacy at 30 seconds. In the model, the response is the post-product application bacterial counts at 30 seconds and predictors are the study products as a fixed effect and the pre-product application bacterial loads as a covariate. The ATE corrected for pre-product application bacterial loads will be estimated from the model and compared to both non-inferiority and superiority criteria. The FDA analysis secondary objectives will be evaluated only when the four co-primary objectives pass both non-inferiority and superiority criteria.

For assessment of the secondary objective (i.e., antimicrobial activity at 30 seconds post application on the abdomen):

1. A non-inferiority criterion with a $0.5 \log_{10}$ margin will be implemented for the ATE of the IP compared to the AC (i.e., the upper two-sided 95% confidence bound of the post-product application bacterial load corrected for pre-product application bacterial load of the IP – AC should be less than $0.5 \log_{10}$).
2. A $1.2 \log_{10}$ superiority criterion will be implemented for the ATE of the IP compared to the NC (i.e., the lower two-sided 95% confidence bound of the post-product application bacterial load corrected for pre-product application bacterial load of the NC – IP should be greater than $1.2 \log_{10}$).

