6.2.2.2 Primary Analysis

A linear regression model for each body site (abdomen or groin) will be used for primary analysis of efficacy at 10 minutes. In the model, the response is the post-product application bacterial counts at 10 minutes and predictors are the study products (IP, AC or NC) as a fixed effect and the pre-product application bacterial loads as a covariate. The average treatment effect (ATE) corrected for pre-product application bacterial loads will be estimated from the model and compared to both non-inferiority and superiority criteria (cf. Table A.3.5).

For assessment of the four primary objectives (i.e., immediate activity at 10 minutes post application on the abdomen and groin for non-inferiority and superiority):

- A non-inferiority criterion with a 0.5 \log_{10} margin will be implemented for ATE of the IP compared to the AC (i.e., if the upper two-sided 95% confidence bound of the post-product application bacterial load corrected for pre-product application bacterial load of the IP-AC is less than 0.5 \log_{10} , the non-inferiority criterion is met).
- A 1.2 \log_{10} superiority criterion will be implemented for the ATE of the IP compared to the NC (i.e., if the lower two-sided 95% confidence bound of the post-product application bacterial load corrected for pre-product application bacterial load of the NC-IP is greater than 1.2 \log_{10} , the superiority criterion is met).

A graph showing the ATE with 95% confidence intervals for post-product log CFU at 10 minutes correcting for pre-product application will be provided for each contrast (cf. Figure C.2.1 created based on the simulated data).

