6.2.2.3 Secondary Analysis

A gatekeeping procedure will be applied: the efficacy analysis for two secondary objectives [30-second (abdomen only) post-product application time point] will be performed only when all four primary

objectives [10-minute (abdomen and groin) post-product application time point] pass the acceptance criteria.

A linear regression model for abdomen only will be used for secondary analysis of efficacy at 30 seconds. In the model, the response is the post-product application bacterial counts at 30 seconds and predictors are the study products (IP, AC or NC) as a fixed effect and the pre-product application bacterial loads as a covariate. The average treatment effect (ATE) corrected for pre-product application bacterial loads will be estimated from the model and compared to both non-inferiority and superiority criteria (cf. Table A.3.6).

For assessment of the two secondary objectives (i.e., immediate activity at 30 seconds post application on the abdomen for non-inferiority and superiority):

- A non-inferiority criterion with a $0.5 \log_{10}$ margin will be implemented for ATE of the IP compared to the AC (i.e., if the upper two-sided 95% confidence bound of the post-product application bacterial load corrected for pre-product application bacterial load of the IP-AC is less than $0.5 \log_{10}$, the non-inferiority criterion is met).
- A $1.2 \log_{10}$ superiority criterion will be implemented for the ATE of the IP compared to the NC (i.e., if the lower two-sided 95% confidence bound of the post-product application bacterial load corrected for pre-product application bacterial load of the NC-IP is greater than $1.2 \log_{10}$, the superiority criterion is met).

A graph showing the ATE with 95% confidence intervals for post-product log CFU at 30 seconds correcting for pre-product application will be provided for each contrast if acceptance criteria are met for all four co-primary objectives (cf. Figure C.2.1 created based on the simulated data). If acceptance criteria are not met for any of four co-primary objectives, the plot for 30 seconds will be removed from the graph as no analysis for 30 seconds is performed.

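### The FDA regressions ignore that each subject carries two products, so their 95% intervals have the wrong variance unless left-right residual correlation is zero; subject-clustered standard errors would correct this

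*SAP*

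**What the plan says.** Protocol 3.3.1 sets the allocation: "Each subject will receive two different study products, one on the right side of the body and one on the left". The block table there lists six product pairs. Each pair of IP, AC and NC is given to 27 subjects per block, and each pair that includes the reference standard (RS) to 16, over four blocks.

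The FDA analysis is one ordinary regression per body region. In SAP 6.2.2.2 (10 minutes, abdomen and groin) the "predictors are the study products (IP, AC or NC) as a fixed effect and the pre-product application bacterial loads as a covariate". Protocol 13.5.3 agrees: "predictors are the study products as a fixed effect and the pre-product application bacterial loads as a covariate". For the secondary objectives SAP 6.2.2.3 says "A linear regression model for abdomen only will be used for secondary analysis of efficacy at 30 seconds", with the same two predictors, and Protocol 13.5.4 matches it. The protocol summary repeats both models ("A linear regression model for each body site (abdomen and groin) will be used for primary analysis of efficacy at 10 minutes"; "A linear regression model for the abdomen will be used for a secondary analysis of efficacy at 30 seconds").

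The sample-size, analysis, multiplicity and missing-data sections mention no subject effect, clustered or robust variance, or left-right correlation. Step 2 of SAP 6.4.1 applies the same routine analysis to each imputed data set. Protocol 4.0 states: "Each subject has four independent product application sites".

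**The concern.** Two sites on one person, sampled on the same day, may well have correlated residuals even after each site's own baseline is in the model. An ordinary regression computes its standard errors as if all sites were unrelated. Its confidence bounds are the sole decision rule for the four co-primary and two secondary FDA objectives (0.5 log10 non-inferiority to AC, 1.2 log10 superiority to NC). If the variance is wrong, the 95% label is wrong, and so is the error rate at each margin. The tipping points inherit the same variance through Step 2 of SAP 6.4.1.

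**Working it through.** **Inputs.** Block table, Protocol 3.3.1. Effects in Protocol 13.1 and SAP Table 3: IP - AC 0.06 (abdomen) and 0.10 (groin); NC - IP 1.58 and 2.31. SDs 1.05 (abdomen) and 1.2 (groin). 280 sites per arm, two-sided alpha 0.05. Protocol 13.1 attaches the SD to each treatment effect and SAP Table 3 to each product; the SAP reading is used here. Rho and arm-specific SDs are not in the documents and are assumed below.

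**1. Reproduce the plan's power, sites independent.** SE = SD x sqrt(2/280): 0.0887 abdomen, 0.1014 groin. Power = Phi(distance to margin / SE - 1.96).
- Abdomen non-inferiority: 0.44 / 0.0887, power 0.9986.
- Abdomen superiority: 0.38 / 0.0887, power 0.9899.
- Groin non-inferiority: 0.40 / 0.1014, power 0.9764.
- Groin superiority: 1.11 / 0.1014, power about 1.

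Using the abdomen values twice (10 minutes and 30 seconds), the product is 0.9986² x 0.9899² x 0.9764 = 0.954, in agreement with the stated > 95%.

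**2. Count the pairs.** Each of IP, AC and NC: (16 + 27 + 27) x 4 = 280 sites. Each tested contrast: 27 x 4 = 108 subjects carry both products, so 108 of 280 sites per arm (39%) are directly paired. In all, 3 x 108 = 324 subjects give two sites to an FDA model and 192 (RS on the other side) give one: 648 + 192 = 840 sites in 516 clusters.

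**3. Variance with equal SDs.** For IP - AC, and likewise NC - IP:

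Var = 2 x SD²/280 - 2 x 108 x rho x SD²/280² = (2 x SD²/280) x (1 - 0.386 x rho).

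The regression reports 2 x SD²/280. With r = sqrt(1 - 0.386 x rho), coverage is 2 x Phi(1.96/r) - 1 and the one-sided level is 1 - Phi(1.96/r).

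| Assumed rho | Coverage | One-sided level | All-six power: planned, clustered |
|---|---|---|---|
| -0.1 | 94.6% | 0.027 | 94.9%, 94.4% |
| 0.1 | 95.4% | 0.023 | 95.9%, 96.3% |
| 0.3 | 96.3% | 0.019 | 96.8%, 97.7% |
| 0.5 | 97.1% | 0.015 | 97.6%, 98.7% |

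The power column multiplies six objectives as if independent, although they share arms and subjects, so it is approximate.

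Baseline eligibility is judged site by site, so some pairs may be broken. With an assumed 70 pairs the factor is 1 - 0.25 x rho, and at rho 0.1 / 0.3 / 0.5 coverage is 95.3 / 95.8 / 96.4% with level 0.024 / 0.021 / 0.018.

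**4. Unequal SDs.** The regression pools one residual variance over three arms. Take IP and AC at 1.05, NC at an assumed 0.8, rho 0.1:
- Pooled variance: (2 x 1.1025 + 0.64)/3 = 0.948.
- True over reported variance for IP - AC: 1.1025 x (1 - 0.0386) / 0.948 = 1.118, so r = 1.057.
- Coverage about 93.6%, one-sided level 0.032.

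The two errors cancel when the NC SD equals 1.05 x sqrt(1 - 1.157 x rho): about 0.99 / 0.85 / 0.68 at rho 0.1 / 0.3 / 0.5. Below that, the non-inferiority interval is too narrow.

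**5. Does clustering repair it?** In a simulation of this layout (516 subjects, 840 sites, baseline covariate, abdomen SD, rho 0.5, 4,000 runs), ordinary intervals covered 97.5% for both contrasts; clustered ones covered 95.6% (IP - AC) and 95.2% (NC - IP). With an assumed NC SD of 0.6, ordinary IP - AC coverage was 92.0 / 93.6 / 94.7% at rho 0 / 0.3 / 0.5, and clustered 95.0 to 95.5%. A larger simulation at equal SDs (40,000 runs per scenario) put clustered coverage at 94.8 to 95.3% and the one-sided level at 0.024 to 0.027.

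**The case against.** The strongest reply is that little is at stake. Under the plan's own equal SDs and non-negative correlation, the error favours caution: no objective passes too easily, power stays above 95%, and the change mainly makes passing slightly easier for the sponsor. Rho appears nowhere in the documents. Each site's baseline is already in the model, so the residual correlation may be small, and at 0.1 coverage is 95.4%. All of that stands, and it limits the weight of the point.

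It does not remove the point, because the reassurance needs both rho of at least 0 and equal arm variances. Equal SDs are a planning input in SAP 3.2, not a result. SAP 6.1.1 sets counts below 1 CFU/cm² to 1, which can affect the active arms differently from saline and is a reason not to take equality for granted.

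A reader might infer three stronger things that the documents do not support:
- **That ignored clustering inflates false passes here, as it often does elsewhere.** The compared products lie on opposite sides of the same subject, so positive correlation lowers the variance of the contrast.
- **That the intervals are therefore always conservative.** Step 4 of the working shows otherwise.
- **That the word in Protocol 4.0 ("Each subject has four independent product application sites") explains the choice of model.** No passage says so. It stands in a description of bilateral application areas and may mean only that they are separate areas of skin.

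**Conclusion.** The mismatch between design and analysis is plain in the documents: paired products, and a model with only product and baseline. The nominal 95% intervals are exact only if residual correlation is zero and arm variances are equal. With equal SDs and an assumed rho of 0.1 to 0.5, coverage is 95.4 to 97.1%, the stated > 95% power is safe, and the gain from correction is accurate intervals and modest precision. With negative rho, or saline sufficiently less variable than the active arms, the non-inferiority interval can be too narrow; the worked example gives about 93.6% coverage and a level of 0.032.

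The pair count and the factor 1 - 0.386 x rho follow from the plan if all 108 pairs are evaluable. Every size rests on an assumed rho or SD. This should be fixed because it governs six decision rules and costs almost nothing, not because a conclusion is in danger. The Health Canada one-sample intervals are unaffected, since a subject has at most one IP site per region.

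**What to change.** Keep the planned regressions, point estimates, margins and sample size. In SAP 6.2.2.2 and 6.2.2.3, Protocol 13.5.3 and 13.5.4, and the protocol summary, state that the confidence intervals for the average treatment effects use robust standard errors clustered by subject. Name the small-sample correction and the degrees of freedom (for example, a finite-sample factor with subjects minus one). Clustered robust errors also allow for unequal arm variances, so one change covers both ways in which the ordinary variance can fail.

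Use the same variance in Step 2 of SAP 6.4.1 and carry it into the pooling in Step 3. In Protocol 4.0, say that sites on one subject may be correlated; this is a wording clarification only.

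The cost is one sentence per model in each place, one wording change and slightly more R code. The method relies on a large-sample variance, which is adequate with about 516 clusters. No new data or extra subjects are needed.

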The application will be randomized so that each study product is applied on an equal number of left and right sides of the body within each block as much as possible. Due to baseline bacterial requirements the mITT data set may be imbalanced with regard to right and left sides upon achieving the minimum number of qualifying body sites.

Site and Sample Time Balance

Each groin and abdomen product application site is divided into four sampling areas and each of these sampling areas is sampled once – one at baseline, one at 30 seconds, one at 10 minutes, and one at 6 hours post product application. Therefore, for any groin or abdomen site there are 24 possible sampling orders.

Overall the following priority order will be used for randomization schedule design:

1. Study product combinations will always be applied with assigned numbers in each block to preserve the 6 potential study product combinations of the four study products.
2. Left/right balance will be preserved – each study product will be applied an approximately equal number of times to each side of the body.
3. Sampling orders will be assigned in blocks of 24 as much as possible. If the final number of subjects is not a multiple of 24 the remaining subjects will be assigned random non-duplicative sample orders from the 24 possible sample orders.
4. The blocking will be adjusted based on the final subject numbers with respect to all three factors at once, with priority using the order listed above.

The Investigator is responsible for ensuring that the randomization is followed. A basic outline of a randomization schedule for the abdominal and groin sites is provided in APPENDIX 2. The final randomization schedule will be prepared by the study statistician before the initial product application.

Subjects will be identified by their initials and a subject number.

Randomized subjects will be assigned numbers ranging from 0001 to a four digit number equal to the total number of subjects needed (sufficient randomization codes will be prepared to ensure sufficient codes are available for the indicated maximum evaluable sample size plus subjects not meeting product application day baseline requirements).

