3.3.2.2 Measures to Control Bias

For this study, several measures are being used to control or reduce potential bias. Those measures include, but are not limited to the following:

- Subject randomization;
- Statistical Analysis Plan lists potential protocol deviations and rules for use of associated data in analysis;
- Products will be labeled with treatment codes (A, B, C, D);
- Data Management Plan outlines steps to prevent Sponsor study team members from becoming aware of treatment codes.

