A baseline screening sample will be collected from each product application area using the Williamson-Kligman scrub cup technique. The screening baselines samples will be taken from site #1 within each product application site on the abdomen (left and right sides) and site #3 within each product application site on the groin (left and right sides). Samples from both the left and right sides of a body region must meet the minimum value indicated in the Inclusion Criteria for the subject to be enrolled into the product application phase of the study for that region. Subjects must qualify on all four abdomen and inguinal sites to be admitted into the treatment phase of the study until such time that one of the anatomical sites has completed the minimal required evaluable sites, then subjects will be screened and treated only on the remaining anatomical site.

Subjects who qualify for the study will be notified and will continue to follow the subject instructions until their participation has been completed. Subjects will again be required to refrain from bathing or showering 72 hours prior to Product Application Day and hair will be clipped, if required.

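### The FDA regressions omit side and sampling position, which the randomization schedule balances; pre-specifying them is a minor, nearly free gain in precision

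*SAP*

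**What the plan says.** SAP 6.2.2.2 fits one linear regression per body site to the 10-minute count, in which the "predictors are the study products (IP, AC or NC) as a fixed effect and the pre-product application bacterial loads as a covariate". For the secondary objectives, SAP 6.2.2.3 states: "A linear regression model for abdomen only will be used for secondary analysis of efficacy at 30 seconds", with the same two predictors. Protocol 13.5.3 and 13.5.4 agree. None of these sections has a term for side of the body or for the position of the sample within the application area.

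Protocol 3.3.1 uses both factors when the schedule is built. On side: "The application will be randomized so that each study product is applied on an equal number of left and right sides of the body". This target applies block by block, where feasible. On order, there are 24 ways to assign baseline, 30 seconds, 10 minutes and 6 hours to the four sampling areas, and "Sampling orders will be assigned in blocks of 24 as much as possible". Side and order rank second and third in the priority list, after the product combinations. The same section adds a caution: "Due to baseline bacterial requirements the mITT data set may be imbalanced with regard to right and left sides".

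Protocol 3.3.2.2 lists randomization among the measures for controlling bias: "For this study, several measures are being used to control or reduce potential bias". It does not mention precision.

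**The concern.** A factor that constrains the allocation normally also enters the analysis model. If it affects the outcome and is left out, balance protects the estimate, but the factor's variance remains in the residual and the reported interval is wider than it need be.

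Three features of this plan make the question reasonable:

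- Baseline and post-application counts at a site come from different sampling areas, so the baseline covariate cannot remove position differences.
- Side balance holds in the schedule but is not assured in the mITT set, which admits individual sites according to their baseline count.
- One area per site has already been scrubbed at screening. Protocol 6.1.4 says "The screening baselines samples will be taken from site #1 within each product application site on the abdomen", and area 3 is used on the groin.

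At stake is the width of the intervals for the four co-primary and two secondary FDA comparisons, and some protection against side imbalance. Groin non-inferiority has the lowest planned power of these criteria, so it has most to gain.

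**Working it through.** **Inputs** (Protocol 13.1, SAP 3.2 and Table 3, SAP Table 1). 280 evaluable sites per arm per body site; two-sided alpha 0.05; SD per product 1.05 (abdomen) and 1.2 (groin); assumed IP - AC of 0.06 and 0.10; assumed NC - IP of 1.58 and 2.31; margins 0.5 and 1.2 log10.

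**1. The plan's own figure.** Distances to the margins:

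- abdomen non-inferiority: 0.5 - 0.06 = 0.44
- groin non-inferiority: 0.5 - 0.10 = 0.40
- abdomen superiority: 1.58 - 1.2 = 0.38
- groin superiority: 2.31 - 1.2 = 1.11

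The standard error of a contrast is SD x sqrt(2/280), which is 0.0887 for the abdomen and 0.1014 for the groin. The model for one body site has 840 sites and four parameters (three product means and one slope), so 836 residual degrees of freedom. Noncentral-t powers are 99.9% (abdomen non-inferiority), 99.0% (abdomen superiority), 97.6% (groin non-inferiority) and about 100% (groin superiority).

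Multiplying gives 96.5% for the four co-primaries. Counting the abdomen pair again for 30 seconds gives 95.4% for all six, which reproduces the stated figure of more than 95%. The Health Canada objectives at 192 sites give 95.6%, and 0.956 x 0.954 = 0.912 reproduces the stated overall figure of more than 90%. None of this takes credit for side or position.

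**2. Effect of adjustment.** Let R2 be the share of residual variance that side and position explain. It is not in the documents, so a range is assumed. The interval is multiplied by sqrt(1 - R2), and the SD in the power formula becomes SD x sqrt(1 - R2).

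| R2 (assumed) | sqrt(1 - R2) | Interval narrower by | Groin half-width | Groin non-inferiority power | All six FDA objectives |
|---|---|---|---|---|---|
| 0 | 1.000 | 0 | 0.199 | 97.6% | 95.4% |
| 1% | 0.995 | 0.5% | 0.198 | 97.7% | 95.6% |
| 5% | 0.975 | 2.5% | 0.194 | 98.1% | 96.5% |
| 10% | 0.949 | 5.1% | 0.189 | 98.6% | 97.4% |

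**3. How large an effect each R2 requires.** A left-right difference d, with sides balanced, contributes variance (d/2)^2. For d = 0.2 log10 that is 0.01, so R2 is 0.01/1.05^2 = 0.9% on the abdomen and 0.01/1.2^2 = 0.7% on the groin. Side alone reaches 5% only at d of about 0.47 (abdomen) or 0.54 (groin). If one of the four positions differs by d, it contributes 0.25 x 0.75 x d^2 = 0.1875 d^2. On the groin, 5% of 1.44 then needs d of about 0.62, and 10% about 0.88.

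**4. Validity without the terms.** A simulation of the IP - AC contrast on the abdomen, with balanced sides, independent sites and R2 from 0 to 13.8%, gave coverage of 95.1% to 95.7% for unadjusted nominal 95% intervals (1,500 runs per setting). The intervals are correct or slightly conservative.

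**5. Side imbalance in the mITT set.** If the proportion of left-side sites differs between two arms by p, and a side effect d remains after baseline adjustment, the contrast shifts by p x d. With assumed values of p = 0.05 and d = 0.2 the shift is 0.01 log10, against a groin half-width of 0.199.

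**6. Cost.** Side takes 1 degree of freedom, post-application position 3 and baseline position 3, so 7 in all: 836 - 7 = 829. If the effects are nil, the t multiplier is unchanged to four figures (1.963).

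**The case against.** The strongest case against the point is that it is an optional efficiency gain with no effect size behind it. The documents report no side or position effect. The screening scrub is at least 72 hours before application (Protocol 6.1), and the areas are marked again that day. Each side has its own baseline sample, so a left-right difference in bacterial load is already partly adjusted. Appendix 2 lists one sampling order per subject for both sides. Where a subject receives both IP and AC (27 x 4 = 108 of the 280 sites per arm), position would then be the same for both and cancel. All of this stands, and it keeps the point minor.

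Two stronger readings are tempting, but the documents do not support them. A reader might infer that the design was built to remove this variance; Protocol 3.3.2.2 gives bias control as the purpose, and 3.3.1 describes balancing only. A reader might also infer that sampling orders are balanced across subjects but not within product. The fourth item of the priority list in 3.3.1 adjusts blocking for all three factors together, and the final schedule is not in the documents, so this cannot be asserted.

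It is also fair to say that these terms leave untouched the fact that each subject contributes two sites. That is a separate matter. A subject term would absorb a shared sampling order in within-subject contrasts, but it would not replace a side term, because side varies within subject.

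What the objection does not remove is the protocol's own warning that the mITT set may be unbalanced by side, together with the negligible cost of adjusting for it.

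**Conclusion.** The point holds as a minor improvement. Both FDA models leave out two factors that the schedule balances, so any variance they cause stays in the residual and any side imbalance in the mITT set is only partly corrected through baseline. For an assumed R2 of 1% to 10%, the gain is intervals narrower by 0.5% to 5.1% and 0.1 to 1.0 percentage points of groin non-inferiority power. The lower end is easier to credit: a left-right difference of 0.2 log10 explains less than 1%. If the effects are nil, there is no gain.

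The omission is not an error that threatens the conclusions. The stated power reproduces without these terms. Type I error is not inflated, because unadjusted intervals are correct or conservative under balance. The baseline counts that decide mITT membership are taken before any product is applied, so side imbalance between arms would be a chance imbalance that the interval already allows for.

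**What to change.** In SAP 6.2.2.2 and 6.2.2.3, add to both models fixed terms for side (left/right), position of the post-application sample (1-4) and position of the baseline sample (1-4). Estimate the same IP - AC and NC - IP contrasts against the same margins.

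State that these terms use the side actually treated and the position actually sampled where a deviation makes them differ from the schedule. SAP Table 4 keeps wrong-side and wrong-sample-site data in the mITT set, so the choice needs to be written down. Align Protocol 13.5.3 and 13.5.4.

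The cost is a sentence or two of text and 7 of about 836 residual degrees of freedom. Scheduled side and position are already in the randomization schedule, and departures are captured as protocol deviations. The terms should be fixed before unblinding, because adding them after an imbalance has been seen would look data-driven.
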